FIH	First-in-human
FSH	Follicle stimulating hormone
GCP	Good clinical practice
GERD	Gastroesophageal reflux disease
Hb	Hemoglobin
HIV	Human immunodeficiency virus
HR	Heart rate
HTR	Holding Time Ratio (%)
IB	Investigator's brochure
ICF	Informed consent form
ІСН	International Council for Harmonization of Technical Requirements for Pharmaceuticals for Human Use
IME	Important medical event
IMP	Investigational medicinal product
IR	Immediate release
ISF	Investigator site file
IUS	Intra-uterine system
LLOQ	Lower limit of quantification
MAD	Multiple-ascending dose
МСН	Mean corpuscular hemoglobin
MCV	Mean corpuscular volume
MedDRA	Medical dictionary for regulatory activities
NCA	Non-compartmental analysis
NCS	Not clinically significant
PD	Pharmacodynamics

Statistical Analysis Plan

CX842A2107

Version 2.0, 04-Oct-2023

Abbreviation	Term
РК	Pharmacokinetics
PK(INR)	Prothrombin complex international normalized ratio
PKAS	PK analysis set
PT	Preferred term
QC	Quality control
QD	Quaque die (once daily)
QRS interval	(ECG) The time required for stimulus to spread through the heart's ventricles
QT interval	(ECG) The time from the beginning of the QRS complex to the end of the T wave
QTcF	(ECG) Corrected QT interval by Fredericia
R _{acc}	Accumulation ratio
RSI	Reference safety information
SAE	Serious adverse event
SAP	Statistical analysis plan
SAR	Serious adverse reaction
SD	Standard deviation
SOC	System organ class
SOP	Standard operating procedures
SUSAR	Suspected unexpected serious adverse reaction
TMF	Trial Master File
T _{max}	Time of occurrence of C _{max}
T _{1/2}	Terminal elimination half-life
V _z /F	Volume of distribution following extravascular administration
WHO	World Health Organization

1. Introduction

This Statistical Analysis Plan (SAP) provides a detailed and technical description of the planned pharmacokinetic (PK) and pharmacodynamic (PD) analyses and statistical evaluations of Cinclus Pharma AB's study CX842A2107: "A phase 1, open label, randomized, parallel-group, single center study to investigate pharmacokinetics and pharmacodynamics (intragastric pH) of linaprazan glurate/linaprazan after single and 14 days repeated oral administration of linaprazan glurate to healthy subjects.".

The SAP is prepared in compliance with the guidelines for Statistical Principles for Clinical Trials (ICH E9).

A full description of the investigational plan, eligibility criteria, assessments, etc. is given in the Clinical Study Protocol (CSP) CX842A2107 v4.0 dated 10MAR2023.

In case this SAP deviates from the statistical analysis described in the CSP, the reason for the deviation and/or alternative or additional statistical analyses will be documented in amendments to the CSP or in this SAP.

2. Study Objectives and Endpoints

This is a Phase I, single-center, open parallel-group, randomized study designed to evaluate the pharmacokinetics (PK), pharmacodynamics (PD), safety and tolerability of single and repeated oral doses of linaprazan glurate at 3 dose levels in healthy male and female subjects.

2.1 Primary Objectives

• To characterize the PK and PD of linaprazan glurate and linaprazan after once daily (QD evening dose) and twice (BID) daily dosing after single and repeated administration of linaprazan glurate.

2.2 Secondary Objectives

• To assess the safety and tolerability after single and repeated doses of linaprazan glurate.

2.3 Exploratory Objectives

2.4 Primary endpoints

- Linaprazan glurate and linaprazan PK parameters after single and repeated administration of linaprazan glurate (when applicable):
 - $\circ~$ Area under the plasma concentration vs. time curve (AUC) at different timepoints: AUC_{0-24}, AUC_{0-12}, AUC_{12-24}, AUC_{24-48}, and AUC_{0-t}.
 - The minimum, end-of dosing interval, maximum and average plasma concentrations C_{trough}, C_{max}, C_{aver}.

Statistical Analysis Plan CX842A2107 Version 2.0, 04-Oct-2023

- Percentage of time gastric pH >4 at Day 1 and Day 14, over a 24-hour monitoring period following linaprazan glurate administration.

2.5 Secondary endpoints

- Additional PK parameters for linaprazan glurate and linaprazan PK parameters (*e.g.*, but not limited to apparent clearance [CL/F], apparent volume of distribution [V/F], accumulation ratio [R_{Acc}], C_{min}, AUC from 0 to infinity [AUC_{inf}] and AUC percent extrapolation [AUC_{extrap%}]).
- Frequency, intensity and seriousness of adverse events (AEs).
- Clinically significant changes in:
 - Electrocardiogram (ECG)
 - o Vital signs
 - Physical examinations
 - Safety laboratory parameters

2.6 Exploratory endpoints

The exploratory endpoints may be reported separately from the clinical study report (CSR).

3. Study Details

3.1 Study Design

This is a Phase I, single-center, open parallel-group, randomized study designed to evaluate the PK, PD, safety, and tolerability of single and repeated oral doses of linaprazan glurate at three dose levels in healthy male and female subjects.

An overview of the study design is shown in

Figure **1**. The overall schedule of events is presented in Appendix Table 1. The detailed schedule of events for individual visits are tabulated in the CSP (see Tables 8.1-2 to 8.1-7 of the CSP for details).

Subjects will be randomized into 1 of 6 dose groups. There will be 6 dose groups as follows:

- No 1: 25 mg linaprazan glurate (1x25 mg oral tablet) QD for 14 days
- No 2: 50 mg linaprazan glurate (2x25 mg oral tablet) QD for 14 days
- No 3: 75 mg linaprazan glurate (3x25 mg oral tablets) QD for 14 days

- No 4: 25 mg linaprazan glurate (1x25 mg oral tablet) BID for 14 days
- No 5: 50 mg linaprazan glurate (2x25 mg oral tablet) BID for 14 days
- No 6: 75 mg linaprazan glurate (3x25 mg oral tablets) BID for 14 days

Subjects participating in the study will attend 7 visits to the clinical research unit (CRU): a screening visit (Visit 1) followed by 6 visits (Visit 2-7). Visit 2, Visit 5 and Visit 7 are residential stays at the CRU and Visit 3, Visit 4, and Visit 6 are outpatient visits. The participants will also be followed by a remote follow-up/end-of-study visit via telephone (Visit 8), 7 days (±2 days) after the final dose.

Figure 1. Overview of study design

3.2 Study population

The subjects participating in this study will be healthy male and female subjects 18–65 (both inclusive) years of age, have with a body mass index (BMI) of 18.5 - 30.0 kg/m² (inclusive), and are eligible for the study. More details regarding the study population, including inclusion and exclusion criteria, can be found in the CSP section 9.

3.3 Randomization and Blinding

Block randomization (block size=6) stratified by gender will be used to generate the randomization list, which will show the assignment of subjects to 1 of the 6 dose groups given in Section 3.1.

The randomization list of the study was be prepared by a statistician at CRS [name], and transferred to the Trial Master File (TMF) for archiving.

As this is an open label study, the dose group to which each subject is allocated will be recorded in the eCRF. A computer-generated randomization list will be created using SAS Proc Plan, SAS Version 9.4 or later (SAS Institute, Inc., Cary, NC) or equivalent program. The randomization list will contain subject number, block, gender, drug holiday period, and dose group.

The randomization list will be generated and kept by CRS.

No blinding procedures will be followed.

3.4 Number of Subjects

3.4.1 Sample Size

Approximately, 116 healthy volunteers are planned to be screened to achieve 72 randomized subjects. An estimated total of 12 subjects will be included per dose level (in total 6 dose groups). If less than 9 subjects are evaluable per dose level, addition of new a subject to replace a discontinued subject can be allowed.

3.5 Subject Replacement

Subjects who consented to study participation but discontinued prior to IMP administration (dosing) may be replaced. Subjects withdrawn after dosing may be replaced at the Sponsor's discretion after consultation with the Investigator.

4. Assessments

The overall Schedule of Assessments is given in Appendix Table 1. Details about each visit and the assessments made during the visit are given in the sections in the CSP that are listed in Appendix Table 1.

4.1 Protocol Deviations

Deviations from the CSP should not occur. If deviations from the CSP occur, the implications and classification (minor or major) of each deviation will be decided and documented at the clean file meeting prior to database lock. If a subject is classified with a major protocol deviation potentially altering the treatment outcome, it will lead to exclusion of data from the PK analysis set and any such case should be clearly justified.

Major protocol deviations include:

- Significant non-compliance with study procedures.
- Any serious unforeseen deviation in dosing of the subjects.
- Vomiting or diarrhea within 6 hours after dosing which could render the plasma concentration-time profile unreliable.
- Intake of prohibited medication that may influence the PK results (i.e., known to interact with the PK of linaprazan glurate).

All protocol deviations will be assessed whether they affect the PK analysis to such an extent that the subject needs to be excluded from the PKAS (see section 5.1.2 for the PKAS definition). This assessment will be performed by the Clinical Pharmacology Specialist and be documented in the final Protocol Deviations Log.

Blood sampling outside of the allowed timeframe will not be considered as a major protocol deviation.

4.2 Demographic and Baseline Characteristics

The demographic and baseline data collected in this trial are gender, age, ethnicity, race, height and weight. BMI will be calculated from height and weight and recorded with 1 decimal point.

4.3 Medical/Surgical History

Medical/surgical history will be obtained by subject interview in order to verify that the eligibility criteria are met. The medical/surgical history will include all relevant diseases and operations within 2 months prior to screening as judged by the Investigator.

4.4 Prior and Concomitant Medications

Prior medications taken within 2 weeks prior to first IMP administration are obtained by subject interview in order to verify that the eligibility criteria are met.

Medications are classified as prior if the stop date was before or on the day of the first dose administration (pre-dose) and as concomitant if ongoing on the day of the first dose administration, stopped after the first dose administration or started after the first dose administration.

Any use of concomitant medication from screening until the end-of-study visit will be documented appropriately. Relevant information (i.e., name of medication, dose, unit, frequency, dose form, route, start and stop dates, reason for use) will be recorded.

4.5 Safety Variables

4.5.1 Adverse Events

An AE is defined as any untoward medical occurrence in a subject administered a medicinal product and which does not necessarily have a causal relationship with this treatment. An AE can therefore be any unfavorable and unintended sign (including an abnormal laboratory finding), symptom, or disease temporally associated with the use of a medicinal product, whether or not considered related to the medicinal product.

Definitions for the different types of AE including the definition for Serious Adverse Events (SAEs), Adverse Reaction (AR), Serious Adverse Reaction (SAR) and Suspected Unexpected Serious Adverse Reaction (SUSAR) are given in section 11.4 of the CSP.

The following variables will be collected for each AE and SAE:

- Start date and time
- Stop date and time
- Whether the AE is serious
- Intensity (Grading using CTCAE v5.0)
- Causal relationship to IMP (Probable, Possible, Unlikely)
- Assessment of outcome (Recovered/resolved, Recovering/resolving, Recovered/resolved with sequelae, Not recovered/not resolved, Fatal, Unknown)
- Action taken with study treatment (Dose increased, Dose not changed, Dose reduced, Drug interrupted, Drug withdrawn, Not applicable, Unknown)

An AE is considered causally related to the use of the IMP when the causality assessment is probable or possible.

AEs will be followed up until resolution or end-of-study visit, whichever comes first.

4.5.2 Laboratory Evaluations

Blood and urine samples for the assessment of safety and eligibility will be collected as shown in Table 3. Safety laboratory values will be specified and documented as Normal, Abnormal NCS (not

clinically significant), or Abnormal CS (clinically significant). Abnormal post-dose findings assessed by the Investigator as CS will be reported as AEs.

Category	Parameter
Clinical chemistry	Alanine aminotransferase (ALT)
	Albumin
	Alkaline phosphatase (ALP)
	Aspartate aminotransferase (AST)
	Bilirubin (total and conjugated)
	Calcium
	Creatinine
	Glucose
	Phosphate
	Potassium
	Sodium
	Urea
Hematology	Erythrocyte count
	Leukocyte count with differential count
	Hematocrit (B-EVF)
	Hemoglobin (Hb)
	Mean corpuscular volume (MCV)
	Mean corpuscular hemoglobin (MCH)
	Platelet count
Coagulation	Activated Partial Thromboplastin Time (APTT)
	Prothrombin Complex International Normalized Ratio (PK[INR])
Jrinalysis (dip stick)	Erythrocytes
	Glucose
	Ketones
	Leukocytes
	Nitrite
	рН
	Protein
	Specific gravity
	Urobilinogen
Statistical Analysis Plan	
CX842A2107	

Table 3. Safety Laboratory Parameters

CX842A2107

Version 2.0, 04-Oct-2023

Category	Parameter
FSH -test (at screening, postmenopausal females only)	Follicle stimulating hormone (FSH)
Pregnancy test (female subjects of childbearing potential only)	Urine pregnancy test.

4.5.3 Physical Examination

A complete physical examination will include assessments of the head, eyes, ears, nose, throat, skin, thyroid, neurological, lungs, cardiovascular, abdomen (liver and spleen), lymph nodes and extremities.

Any abnormalities will be specified and documented as CS or NCS. Abnormal post-IMP administration findings assessed by the Investigator as clinically significant will be reported as AEs.

4.5.4 Vital Signs

Vital signs will include systolic and diastolic blood pressure, pulse rate and body temperature. Any vital signs outside of normal ranges will be specified and documented as CS or NCS. Abnormal post-dose findings assessed by the Investigator as CS will be reported as AEs.

4.5.5 ECGs

A 12-lead ECG will be recorded pre-IMP administration and at 24 hours post IMP-administration during visits 1, 2, 5 and 7.

The following variables will be recorded:

- Resting Heart Rate (HR)
- PQ/RR
- QRS
- QT
- QTcF

Any abnormalities will be specified and documented as CS or NCS. Abnormal post-IMP findings assessed by the Investigator as CS will be reported as AEs.

4.6 Pharmacokinetic Assessments

Blood sampling time points for PK analyses and their allowed sampling time windows are detailed in section 11.3.1 of the CSP. The actual blood sampling time points will be recorded in the CRFs.

Plasma samples for determination of plasma concentrations and PK characterization of linaprazan glurate and linaprazan will be analyzed by the same set of a by means of a

The PK

parameters to be determined are listed and defined below. For further details regarding the calculation of these parameters, see section 5.6.

4.6.1 Primary and secondary analyses

PK parameters:

When applicable, the following PK parameters will be obtained or calculated from the plasma concentration-time data of linaprazan glurate and linaprazan after QD or BID dosing with linaprazan glurate:

- AUC_{inf} (the area under the concentration-time curve from time zero extrapolated to infinity)
- AUC_{extrap%} (% extrapolated AUC)
- AUC_{0-t} (area under the concentration-time curve from time zero to t=last)
- Partial AUC (area under the concentration-time curve from time zero to t=12h and 24h, from 12h to 24h, and from 24h to 48h)
- C_{max} (maximum observed concentration)
- C_{min} (minimum observed concentration)
- C_{trough} (Concentration before next dose)
- C_{aver} (average concentration in a 12 or 24 h dose interval)
- T_{max} (time to maximum observed concentration)
- T_{1/2} (terminal half-life)
- CL/F (apparent total clearance)
- V/F (apparent volume of distribution)
- R_{acc} (accumulation ratio for C_{max} and AUC in a 12 or 24 h dose interval)

Additional PK parameters may be determined, such as:

- λ_z (elimination rate constant)
- T_{lag} (Delay between the time of dosing and the time of appearance of plasma concentration)
- AUC_{tau} (the area under the concentration-time curve in a dosing interval)

4.6.1 Exploratory analyses

5. Analysis Methods

All statistical analyses will be performed using SAS[®] (Version 9.4 or higher, SAS Institute Inc., Cary, NC, USA).

All PK analyses will be performed on individual plasma concentration-time data by noncompartmental analysis (NCA) using the software Phoenix WinNonlin[®] 8.3 or higher (Certara Inc, Princeton NJ, United States).

All statistical and PK analyses will be performed after this SAP is finalized and approved, the Clean File Report including decisions on analysis sets has been signed, and the database has been locked.

5.1 Analysis Sets

5.1.1 Full Analysis Set (FAS)

The full analysis set (FAS) will consist of all subjects who have been randomized and received at least 1 dose of IMP and who provided at least 1 post-baseline assessment of data.

The FAS will also be used for all safety analyses.

5.1.2 PK Analysis Set (PKAS)

The PK analysis set (PKAS) will consist of all subjects who received at least 1 dose of linaprazan glurate and provided an evaluable plasma concentration profile, and who have no AEs or protocol deviations judged to affect the PK analysis. Individual PK values may be excluded from the analysis as specified in section 5.6.

5.1.3 PK/PD Analysis Set (PK/PDAS)

The PK/PD Analysis set (PK/PDAS) is a subset of the PK Analysis Set, excluding subjects without an evaluable and appropriate pH profile.

5.2 General Principles for Presenting Study Data

5.2.1 Presentation of Data

Continuous data will be summarized using descriptive statistics where the following statistics will be reported:

- Number of observations (n),
- Arithmetic Mean
- Arithmetic Standard deviation (SD),
- Median,
- Min. and Max.
- Geometric Mean for log-normal PK parameters
- Geometric Coefficient of Variation (CV%) for log-normal PK parameters

Categorical data will be presented as the number and percentage of subjects or observations in each category.

Percentages will be based on number of subjects with data at a certain time point in the analysis set of interest except for presentations of medical history, medications, and AEs where the percentages will be based on the number of subjects in the study population.

In general, all data will be listed. All summary tables will be structured with a column for each dose group and will be annotated with the total population size relevant to that table/dose group, including any missing observations.

A separate TLF plan will be prepared by the study statistician.

5.2.2 Calculation of PK Data

Individual and mean PK profiles for concentrations of linaprazan glurate and linaprazan will be plotted in Phoenix[®] WinNonlin[®] and reported for all subjects in the PK analysis sets. Mean concentration data will be plotted against scheduled (nominal) sampling times while individual concentration data will be plotted against actual sampling times.

PK concentration data

All individual PK concentrations will be presented in listings included in the appendices of the CSR. These data will be presented and analyzed with the same precision as the source data provided by the bioanalytical laboratory.

PK parameters

The derived parameters will be listed individually by subject and summarized by treatment using descriptive statistics. PK parameters and actual elapsed sample collection times will be rounded for reporting purposes in by-subject listings.

PK data will be presented by treatment using summary statistics with number of measurements, arithmetic mean, SD, as well as median, minimum and maximum values. For the PK parameters AUC_{inf} , AUC_{0-t} , partial AUCs, C_{max} , C_{aver} , C_{trough} , and C_{min} the geometric mean and geometric coefficient of variation (CV%) will also be presented. For the PK parameters T_{lag} and T_{max} , only the median, minimum, and maximum values will be presented. For the PK parameter R_{acc} and $AUC_{extrap\%}$, the geometric mean and CV% will also be presented. All data will be listed by treatment and subject.

Individual and mean linaprazan glurate and linaprazan plasma concentrations will be plotted against time for each dose group.

In export datasets, PK parameters will be provided with full precision, and will not be rounded. Descriptive statistics of PK parameter data will be calculated using full precision values and rounded for reporting purposes only.

5.2.3 Calculation of PD data (intragastric pH)

The raw pH-data presents pH values for each second of the patient's pH recording period. In the derivations, subject specific time windows based on subject's first dose of the day were used.

For the calculation of Holding Time Ratio (HTR), both raw pH-data (every second measurements) and the raw data compressed into 10-minute periods by calculating the median for each 10-minute period, were used. For all other analyses described in section 5.7 the 10-minute median values were used.

Before the described derivations, the raw pH-data was processed according to the rules defined in the SAP addendum ("Process to manage issues associated with the pH-metry recordings and data").

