5.7 Summaries of Intragastric pH-metry

The Full Analysis Set for pH measurements is defined in the SAP addendum. pH measurements will be analyzed as per SAP addendum Full Analysis Set #2 "Statistical analysis of either channel 1 or 2 depending on which is deemed to be showing intragastric pH. Exclusion of "air measurements" is applied."

Exploratory analyses will be performed based on Full Analysis Sets #1 and #3 in the SAP addendum.

Descriptive statistics of HTR pH >4, pH >5, and pH >6 over a 24-hour period during baseline, day 1, day 14 and day 15, will be presented by dose group.

A Mixed Model for Repeated Measurements (MMRM) will be utilized to analyze the percentage of time with intragastric pH >4, pH >5, and pH >6 (each pH cut-off separately), from now on referred to as Holding Time Ratio (HTR). The model will include the dose group, day (day 1, day 14) and the interaction between the dose group and day as fixed effects, the corresponding baseline HTR as a covariate and subject as a random effect. Least Squares Means (LSMs), together with their corresponding 95% confidence intervals (CI) will be used to estimate the HTR for each dose group and day.

The LSMs of HTR pH >4, pH >5, and pH >6 will also be graphically displayed together with their corresponding 95% CIs by visit (day 1 and day 14) for each dose group. As a sensitivity analysis a MMRM-model (separately for the three pH cutoffs) excluding the baseline covariate will also be fitted to support the results from the primary statistical model.

The trajectories (profiles) for the average 24-hour intragastric pH (pH values averaged over subjects for each 10-minute median value) will be plotted for day 1 and day 14 separately. The plot for each day will show the mean 24-hour intragastric pH for the six dose groups and baseline.

Bar plots for the frequencies of subjects showing the HTR (0-60, 60-80, 80-85, 85-90, 90-95, 95-100) with gastric pH >4, pH >5, and pH >6 over a 24-hour period during baseline, day 1, day 14 and day 15, will be presented by dose group. The horizontal axis of the bar plot will represent categorized HTR with gastric pH >4, pH >5 or pH >6 over a 24-hour period.

Descriptive statistics will be presented for the mean intragastric pH 0-12 hours and 12-24 hours and 0-24 hours after dose (mean within individuals over 0-12 hours, 12-24 hours and 0-24 hours after dose morning dose for BID, evening dose for QD) for days 1 and 14 by dose group.

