The mean intragastric pH 0-12 hours, 12-24 hours and 0-24 hours after dose (morning dose for BID, evening dose for QD) for day 1 and 14 will be plotted together and separately, with their corresponding 95% confidence intervals in a graph displaying the mean values by visit for each dose group.

5.7.1 Relationship between plasma concentration of Linaprazan and intra gastric acid secretion (pH)

To illustrate the association between pH and the linaprazan concentration, scatterplots with pH on the y-axis and a horizontal line to illustrate pH >4, and linaprazan concentration in the x-axis will be plotted. These scatterplots will be presented as follows: i) QD dosing groups, ii) BID dosing groups, iii) all dosing groups. All dosing groups in one scatterplot will be presented for Day 1, Day 14 and together. All measurements from within <2h after first dose on Day 1 will be omitted from the scatter plots.

Line plots with two y-axes (primary y-axis: pH, and secondary y-axis: plasma concentration of linaprazan) against time will be presented for the average pH and average concentration data added with error bars for the standard errors of the means. Three separate plots will be generated, i) QD dosing groups, ii) BID dosing groups, iii) all dosing groups. In the plots both the means pooled over the mentioned dosing groups and the mean for individual dosing groups will be presented for Day 1, Day 14 and together.

Also, scatterplots relating HTR for pH >4 and pH >5 versus linaprazan exposure parameters (AUC, Cmax and Cmin) (ref: Scarpignato et al 2023) will be produced, to explore which PK-parameter would be most relevant. The HTR response within each subject will be explored as well. Three separate plots will be generated, i) QD dosing groups, ii) BID dosing groups, iii) all dosing groups. All plots will be presented for Day 1, Day 14 and together. All measurements from within <2h after first dose on Day 1 will be omitted from the scatter plots.

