5.8 Changes to Planned Analysis

No changes for the main protocol planned analysis have been made. The formal analysis of the pH data and the association between the concentration and pH data was not defined in the protocol but introduced only in the SAP. Also, the PK/PD analysis set is a new analysis dataset defined only in the SAP.

6. References

- 1. Clinical Study Protocol CX842A2107. Final version 4.0 dated 10MAR2023.
- 2. Statistical Principles for Clinical Trials (ICH Topic E 9). EMEA. September 1998, CPMP/ICH/363/96.

7. Appendix

Table 1. Overall schedule of events

Visit → Assessment↓	CSP Section	Visit 1 Screening	Visit 2 Residential	Visit 3 and Visit 4 Outpatient	Visit 5 Residential	Visit 6 Outpatient	Visit 8 Telepho follow-u	
Day→		Day -28 to Day -2	Day -2 to 2	Day 5 and Day 10	Day 14 to Day 15	Day 16	7 days (days) po dose ¹	
Informed consent	11.2.1	X						
Eligibility criteria	9.4, 9.5	X	X ²					
Demographics	11.2.3	X						
Weight/height (BMI)	11.2.4	X						
Medical/surgical history	11.2.5	X						
HIV, Hep B and C test	11.2.7	X						
FSH test ³	11.2.8	X						
Pregnancy test	11.2.9	X	X					
Urine drug screen	11.2.10	X	X ⁴					
Alcohol test	11.2.11	X	X ⁴					
Screening for Helicobacter Pylori	11.4.5	x						
Safety laboratory profile	11.4.3	X	X	Х	Х	X		
Vital signs ⁵	11.4.4	Х	x		Х			

Statistical Analysis Plan

CX842A2107

Version 2.0, 04-Oct-2023

Visit → Assessment↓	CSP Section	Visit 1 Screening	Visit 2 Residential	Visit 3 and Visit 4 Outpatient	Visit 5 Residential	Visit 6 Outpatient		Visit 8 Telephone follow-up
Physical examination	11.4.2	Х	Х		Х			
12-lead safety ECG	9.9	Х	Х		Х			
Randomization	10.5	X ⁶						
IMP administration ⁷	11.3.1		X	X	X			
PK blood sampling ⁸	11.3.2		X	X	Х	X		
Intragastric pH measurement	9.6.1		x		х			
Standardized meals	10.5		X		X			
Hand-out of linaprazan glurate ⁹	10.7		x					
Compliance check	N/A				X			
Overnight stay in clinic	11.2.12		X		X			
Baseline symptoms ¹⁰	11.4	X						
AEs ¹¹	9.6.2			X				
Prior and concomitant medications	11.2.1	X						

BMI: Body mass index. CSP: Clinical study protocol. FSH: follicle stimulating hormone. HIV: Human immunodeficiency virus. IMP: Investigational medicinal product. PK: Pharmacokinetic.

- 1. A final remote follow-up visit (Visit 8) will be conducted via telephone 7 days (±2 days) after the final dose of IMP, or after early withdrawal, to follow-up on AEs and concomitant medications.
- 2. Confirmation of eligibility prior to start of baseline pH-measurement.

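### Does the SAP need to say whether per-second or 10-minute-median HTR leads for the primary pH endpoint?

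*SAP*

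**What the plan says.** Section 2.4 lists among the primary endpoints "Percentage of time gastric pH >4 at Day 1 and Day 14, over a 24-hour monitoring period". Section 5.7 gives this quantity the name HTR and applies it to three cut-offs (pH >4, >5 and >6); only pH >4 is in the visible primary list.

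Section 5.2.3 states how HTR is obtained: "For the calculation of Holding Time Ratio (HTR), both raw pH-data (every second measurements) and the raw data compressed into 10-minute periods", the compression being the median of each period. It adds: "For all other analyses described in section 5.7 the 10-minute median values were used". It also says that the recordings were first processed under the rules of the SAP addendum.

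In section 5.7 the mixed model "will be utilized to analyze the percentage of time with intragastric pH >4", and its least squares means with 95% confidence intervals "will be used to estimate the HTR for each dose group and day". The baseline covariate is the corresponding baseline HTR. Section 5.7 ranks two other choices. pH analysis set #2 leads, with #1 and #3 exploratory, and a model "excluding the baseline covariate will also be fitted to support the results from the primary statistical model" is the sensitivity analysis. Section 5.7.1 adds "scatterplots relating HTR for pH >4 and pH >5 versus linaprazan exposure parameters". None of these places names a time resolution.

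Section 5.8 records that "The formal analysis of the pH data and the association between the concentration and pH data was not defined in the protocol" and was introduced in the SAP.

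**The concern.** A primary endpoint normally has one lead derivation, fixed in advance. Here the same name covers two quantities. Per-second HTR is the share of seconds above the cut-off. The 10-minute version is the share of 10-minute periods whose median is above it. A short dip below pH 4 counts in the first and can vanish from the second.

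For pH >4 there are 6 dose groups × 2 days = 12 least squares means, and each could exist in two versions with neither marked as the main one. The SAP ranks alternatives elsewhere in section 5.7, so the silence on resolution stands out. By section 5.8, the formal pH analysis cannot simply be looked up in the protocol. What would be at stake is which estimate is quoted as the primary result, and the freedom to pick the more favourable one.

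**Working it through.** The SAP gives no figure for the difference between the versions, so there is none to reproduce. The check has three parts.

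**1. Exact arithmetic on the definitions.** A 24-hour recording has 86,400 seconds and 24 × 6 = 144 ten-minute periods.
- Step size of per-second HTR: 100/86,400 = 0.0012 points.
- Step size of 10-minute HTR: 100/144 = 0.69 points.
- If 60% of the seconds in every period exceed pH 4, per-second HTR is 60% and 10-minute HTR is 100%. If 40% do, the results are 40% and 0%.

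So the versions can differ widely in principle. A period changes sides only when more than half of it, 5 minutes, lies on the other side of the cut-off. The gap therefore depends on how long the excursions last.

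**2. Size under assumed run lengths.** The SAP gives no excursion lengths, so these are assumptions. One-second states above or below the cut-off were simulated for 24 hours with exponential runs, 1,000 recordings per setting. The stated mean run is that of the dips (true HTR 80% and 90%) or of the runs above the cut-off (true HTR 30%). The mean of the other runs was set to give the true HTR.

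Gap = 10-minute HTR minus per-second HTR, paired within recording, in points:

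| Mean run (min) | 1 | 2 | 3 | 4 | 5 | 10 | 30 |
|---|---|---|---|---|---|---|---|
| True HTR 80% | +15.4 | +9.8 | +6.8 | +4.8 | +3.5 | +1.3 | +0.2 |
| True HTR 90% | +8.9 | +6.0 | +4.1 | +2.9 | +2.2 | +0.7 | +0.1 |
| True HTR 30% | −17.6 | −10.6 | −7.2 | −5.2 | −3.8 | −1.4 | −0.2 |

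The largest standard error is 0.071 points. A repeat with separate code, a new seed and 400 recordings per setting agreed to within about 0.3 points. Gaps above 5 points need mean runs of at most 3 minutes (80%), 2 minutes (90%) or 4 minutes (30%).

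A different assumed model used a slowly drifting pH plus fast noise, with mean pH from 3.5 to 5.5. It gave mean gaps from −5.2 to +10.3 points. The size follows the chosen model; neither model describes this trial's data.

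**3. Reading the passages together.**
- The sentence on all other analyses in section 5.7 follows the HTR sentence. It most naturally covers non-HTR outputs such as pH profiles and mean pH, so it does not make the 10-minute version lead.
- Sections 2.4 and 5.7 both define the quantity as a percentage of time. Per-second HTR is that quantity directly; the 10-minute version approximates it.
- Section 5.2.3 computes both. Its plain reading is that HTR is available at both resolutions, and nothing says that one would be withheld.
- Section 5.7 asks for least squares means with confidence intervals. The visible text sets no between-group test, alpha or success rule on HTR.
- The addendum is section 8 of this SAP. Section 5.3.1 says that it guides the handling of pH recordings for analysis and reporting, and section 5.7 shows that it defines the three pH analysis sets. Its text is not available here, so it cannot be counted as silent. The same holds for the separate TLF plan mentioned in section 5.2.1.

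**The case for a change.** The best case for a change is that this is a primary endpoint and the remedy is a sentence or two. In the assumed scenarios the 10-minute version moves HTR away from 50%, lowering low values and raising high ones, so contrasts between groups or against baseline can look larger. The upper bar-plot categories in section 5.7 are only 5 points wide. In the drift-plus-noise model with mean pH 5.0 to 5.5, between 21 and 56 of 60 simulated subjects changed category. Section 5.2.3 is also written in the past tense, although section 5 places all analyses after SAP approval, so one could ask when the choice was made.

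Part of this stands. No visible passage ranks the two versions, they are not interchangeable, and naming a lead would be tidy. The rest carries less weight. The category counts come from assumed noise, and the bar plots are descriptive. The past tense does not show that results had been seen; the drafting is loose elsewhere too, as in section 3.3. The choice of lead is also partly preference: per-second data match the endpoint wording but keep brief signal noise, which a median smooths.

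**Conclusion.** The observation is accurate, but it does not call for a change. It concerns a missing label in an open-label Phase 1 study whose pH results are presented as estimates with confidence intervals. An analyst following the plan derives HTR both ways, and the endpoint wording leads to the per-second version for the headline figure. The natural match for the baseline covariate is the version used as outcome, since the plan calls it the corresponding baseline HTR.

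The possible difference runs from 0.1 to 17.6 points in absolute value in the run-length scenarios, and is at most 1.4 points once mean runs reach 10 minutes. Those figures rest wholly on assumed excursion lengths, and the real gap may be negligible. The conclusion also rests on two features of the visible text: no decision rule depends on HTR, and the addendum and TLF plan, either of which could name the lead, cannot be inspected. If a formal test or success threshold were attached to HTR, the resolution would need to be fixed with it.
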